To address the needs of our patient population, bilingual and bicultural UCLA fieldwork staff will be trained in the recruitment protocol approved by the UCLA IRB while concurrently maintaining PCORI patient centeredness in mind. Research assistants will be certified by the project manager and Principal investigator to carry out the recruitment protocol as follows: Research assistants will be assigned quadrants of the waiting rooms to observe, systematically approach and screen all patients in the waiting rooms. A research assistant (RA) will directly approach adult patients and identify themselves and their UCLA affiliation. The research staff will then introduce the study to the patient. If the patient provides verbal consent to continue with the screening questions, then the RAs will proceed with the screening questions. The RA then explains that 18 statements would be read to them. The statements will be read in 4 groups of 2 to 5 statements each. After each group of statements the patient will be asked to respond yes or no to the group of questions as a whole as a strategy to ensure confidentiality even if another patient in the waiting room were to eavesdrop. If the patient states that any of the statements applies to him or her, then they will be told that they are ineligible to participate in the study, will be thanked and exited from the study. The exclusion screening statements are as described below in Table 3.

Table 3. Exclusionary Screening Statements

GROUP ONE
1. I am younger than 18.
2. I live outside the Long Beach area.
3. I am planning on moving away from the Long Beach area in the next 12 months.
4. Another member of my household is a participant in this weight loss study.
5. In the last week, I had more than [if men: 5; if women or 65+ years old: 4] glasses of beer or other alcohol that I drank on one occasion.
GROUP TWO

Patterned after protocol published online in association with Appel et al. (2011)¹⁵

6. I have experienced intentional or unintentional weight loss in the last 6 months [>5% of body weight].
7. I am taking or have taken a weight loss medication/prescription medication likely to cause weight gain or weight loss.
8. I am currently taking insulin.
9. I had a heart attack in the last 12 months.
10. I had treatment for cancer.

GROUP THREE

11. I have a condition that limits what I eat and how much I exercise.
12. I had or plan to have bariatric surgery (stomach stapling).

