10. RANDOMIZATION AND MASKING

Randomization

Randomization. As mentioned above in describing the use of REDCap in recruitment, if all measures indicate that the patient remains eligible, a programmed application in REDCap will generate a random assignment to experimental condition for the patient at the end of the screening assessment. The lifestyle change coaches can look up in REDCap's database the study participants assigned to their condition. The coach will then call the patient and arrange for the first coaching session, if appropriate. The research assistants will be kept ignorant of the patient's assignment to experimental condition, to reduce the chance for bias. Of necessity, the behavior change / lifestyle change coaches will be aware of the patient's experimental assignment but will be instructed to follow the protocol carefully, so as not to introduce any personal bias.

Masking

Trial participants will know their intervention assignments, as will the community health worker staff that are involved in delivering the interventions. However, UCLA fieldwork staff involved in follow-up data collection will be kept masked to participants' randomization assignments.. At the conclusion of the trial, participants will receive a summary of clinically relevant measurements. .

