The budget includes the telephone lines for the community health workers, to facilitate their telephone and in-home visits with study participants. The budget also includes the cost of mileage incurred while making in-home visits. Because many patients may be prevented from attending the group health education because of the cost of transportation to the group education event or the cost of childcare, each participant attending the health education will receive \$10 towards deferring the transportation cost and the participant's infant children will be provided free child care. The group education will be open to participation by family members, including spouses and children old enough to benefit from the education.

The Calorie-Counting (CC) Lifestyle Coaching Intervention Approach, as adapted by Wadden et al. (2011) from the Diabetes Prevention Program (DPP-like)

CC Behavior Change Goals. The goals of this intervention are to induce a loss of 5% or more of initial weight through energy restriction by counting calories, limiting daily intake to prescribed amounts and increasing participants' physical activity to > 150 minutes per week and to maintain these improvements over 12 months. These goals will be achieved by providing participants a program of lifestyle modification, delivered by a community health worker lifestyle coach, with encouragement from the patient's primary care provider (PCP).

Description and delivery of the CC intervention. Participants in this group will meet with their PCPs on the same schedule as those in the MyP group and receive the same attention for their comorbid conditions, as well as the weight management handouts. Participants in this condition will receive a program of lifestyle modification based on the curriculum used in the Diabetes Prevention Program (DPP). The lifestyle modification program will be delivered to participants during regularly scheduled phone calls conducted by community health worker lifestyle change coaches. We elected to use the DPP materials because they have been shown to be effective across a wide range of participants and provide tailored dietary menus for African Americans and other ethnic minorities. The DPP materials have been adapted for delivery in primary care practice by community health worker lifestyle change coaches and have obtained a loss of approximately 3.8% of initial weight during 6 months of treatment.¹⁴

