1. Daily write down: minutes of moderate intensity exercise in bouts of 10 or more minutes and all food and beverages consumed. Look up and record calories of each item consumed on hard copy of Tracking Form 3 days per week. Bodyweight need be recorded only once each week.
2. During first few weeks: Weekly reporting to lifestyle change coach of daily average calories consumed, average minutes of moderate to vigorous physical activity expended for the week, average body weight for the week, and delivery of food records for the week.

During weight maintenance (i.e. > 5% weight loss achieved), participants are advised to:

1. Daily write down: minutes of moderate intensity exercise in bouts of 10 or more minutes and body weight.
2. Write down all foods, beverages and calories consumed 3 days/week.
3. During first few weeks: Weekly reporting of daily activity to lifestyle change coach. To include: average body weight for the week, number of days of food records were kept, total calories consumed per day, total minutes of moderate intensity physical activity expended each day.

Format, frequency, and duration of CC participant contact. CC participants receive telephone calls from lifestyle change coaches throughout the study to encourage recording of body weight, daily calories, food intake, and daily physical activity activity. Except for weeks when group health education is offered, calls / home visits will be encouraged to be one session per week for months 1-3. Each call is expected to take 15-20 minutes.

Primary Care Provider role. At the screening visit as well as subsequent routine medical visits, these participants will be encouraged by their PCP to engage actively in whatever intervention they were assigned to.

Outline of the Content of the Lifestyle Change Sessions for MyPlate Participants:

For MyPlate participants, the group health education content will include: 1) Tips on making use of the physical activity equipment in the gym-in-the-bag; 2) Tips on how to shop for fresh produce, low-fat/non-fat dairy, lower sodium food products, whole grains and DASH-type mixed dishes. Also discussion of the importance of community resources for sustaining prescribed levels of physical activity and good adherence to DASH-style eating.

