Primary Care Provider role for MyPlate participants. At routine medical visits, MyPlate participants will be encouraged by their PCP to actively engage in the intervention. Research staff will provide PCP with a report of their patient's progress and that provides key behavioral recommendations for the PCP to reinforce.

Standardizing Delivery of the Intervention.

The function of the Intervention Director is to monitor the delivery of the intervention on a weekly basis, provide corrective feedback if and when the community workers / lifestyle change coaches diverge from the intervention protocol, and learn from the coaches' weekly debriefings which solutions to lifestyle change challenges are effective. The lifestyle change coaches will meet weekly with the Intervention Director as part of a weekly "Learning Community" to problem

solve how to get patients to adhere better to both the dietary and the physical activity prescriptions in the CC and MyPlate conditions. The coaches will be well-trained in what should be covered in each of the 7 phone sessions as well as what should be covered in the two in-home visits.

All intervention print materials and study measures will be translated into Spanish, back-translated to ensure accuracy and subjected to cognitive interviews, to ensure that they communicate the same constructs as the corresponding English print materials and study measures. Drafts of intervention print materials and study measures will be reviewed in focus group discussions to ensure community acceptance of the final versions.

Interventionists/Delivery Systems

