We will employ a number of strategies to facilitate retention. First, a prime criterion for selecting intervention staff will be the individual's ability to engage participants. Experience from previous long-term trials makes it clear that participant retention is maximized when they bond closely with staff. Second, all communication with participants will be designed to maximize the participant's sense that the study understands the challenges involved in efforts to lose weight, and that the staff is committed to make dealing with these challenges as easy as possible. Third, the interventions themselves are designed to help participants succeed in their efforts to lose weight, thus providing substantial reinforcement for staying in the study. In addition, the regular monitoring reports study participants will receive are also designed to highlight the positive changes participants have made. Fourth, the logistic barriers to participation in the study will be minimized. For both interventions, sessions will be held in the evenings and weekends. Finally, PCPs will serve as intervention ‘cheerleaders’, encouraging participants to stay in the study and to maintain their weight loss efforts. Towards the end of the trial, a debriefing of PCPs will occur in order to assess their contributions to the MyPlate and CC intervention and identify strategies that might improve the effectiveness of the interventions.

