12. SAFETY MONITORING

The study will monitor participant safety. One aspect of safety monitoring is to evaluate potential study participants at screening to determine whether it is safe for them to participate in the interventions. This will be done in collaboration with the participant's PCP, who will have received information and training about the trial, particularly its eligibility criteria, interventions, and safety monitoring procedures. In this trial, primary care will be provided by the participant's PCP, not by study personnel. A second aspect is monitoring the safety of enrolled participants. If a participant develops a medical problem, the safety of continuing or resuming the intervention will be ascertained by the participant's PCP in collaboration with a study clinician. The

Patterned after protocol published online in association with Appel et al. (2011)¹⁵

investigators met weekly during the active intervention phase with the community health workers/ change agents to discuss, among other things, evidence of adverse events. Surveillance for serious adverse events and other relevant clinical events occurred as needed. Third, if we became aware of medical problems from abnormal physical measurements, such as blood pressure assessment, we referred the patient to her primary care physician and follow-up to make sure that she completed the referral. Results of routine physical measures obtained as part of study visits will be provided to the participant's PCP with patient's consent. In addition, the staff were prepared to address immediately items meeting the criteria for 'Alert Values' listed in the table below. A designated study clinician with appropriate expertise will be designated as the 'Health Safety Officer' and will review medical eligibility criteria and clinical measures as needed. The Safety Officer will also be responsible for reviewing and reporting SAEs for the site, as detailed elsewhere. This person or persons will have appropriate back-up during vacations or other absences to provide 24/7 medical safety coverage for the duration of the study.

Potential Risks

The following sections describe potential risks associated with the study along with procedures to minimize risk.

Physical Activity

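### As written, the MyPlate arm's PCPs receive progress reports with recommendations to reinforce and no equivalent is given for Calorie Counting: a co-intervention outside the stated contrast, and a possible masking risk

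*Combined protocol and SAP*

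**What the plan says.** Section 11 describes the PCP's part separately for each arm.

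- **CC** (Primary Care Provider role): at the screening visit and later routine visits, "these participants will be encouraged by their PCP to engage actively in whatever intervention they were assigned to". Nothing further is provided.
- **MyP** (Primary Care Provider role for MyPlate participants): PCPs encourage engagement at routine visits, and then: "Research staff will provide PCP with a report of their patient's progress and that provides key behavioral recommendations for the PCP to reinforce".

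Other text on PCP involvement:

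- The description of CC delivery in Section 11 says CC participants "will meet with their PCPs on the same schedule as those in the MyP group and receive the same attention for their comorbid conditions", and also mentions weight management handouts.
- The retention subsection of Section 11 gives PCPs in both arms the task of "encouraging participants to stay in the study and to maintain their weight loss efforts".
- Section 12 says: "Results of routine physical measures obtained as part of study visits will be provided to the participant's PCP with patient's consent". This is not limited to one arm.

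On masking, Section 10 says: "The research assistants will be kept ignorant of the patient's assignment to experimental condition, to reduce the chance for bias". It adds that "UCLA fieldwork staff involved in follow-up data collection will be kept masked to participants' randomization assignments".

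**The concern.** The trial asks which of two behavioural strategies clinics should feature, and it matches the arms on number and type of coaching contacts. A clinician feedback loop supplied to one arm is a second difference between them, and the plan does not present it as part of what is being compared.

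The protocol itself treats this kind of support as active. The Background justifies the number of contacts partly by the motivational value of continued monitoring by health professionals. The theory subsection of Section 11 counts encouragement from medical personnel among the things that reinforce behaviour change, and it does so when describing the CC approach.

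The outcomes exposed include those on which MyP is hypothesised to do better, such as self-efficacy and satisfaction with the programme. For weight, the stated hypothesis is similar declines in the two arms. Extra MyP support could therefore help to produce a difference, or help to produce similarity that the diets alone would not have given.

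The second issue is masking. Anyone who prepares a report that exists for one arm only knows the participant's arm. For low-literacy patients a research assistant administers the hunger question, which is the primary patient-centred outcome, so knowledge of the arm among assessors would matter.

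**Working it through.** No arithmetic applies to the main point. The check is a side-by-side reading.

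**Step 1: compare the two PCP-role paragraphs.**

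| Element | CC | MyP |
|---|---|---|
| PCP encouragement at routine visits | Yes | Yes |
| PCP encouragement at the screening visit | Stated | Not stated in this paragraph |
| Progress report to the PCP | Not mentioned | Stated |
| Key recommendations for the PCP to reinforce | Not mentioned | Stated |

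The screening-visit row is probably a drafting difference, since the Background expects PCPs to encourage all qualifying patients at enrolment. No comparable text elsewhere resolves the last two rows.

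**Step 2: look for an equivalent for CC elsewhere.**

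- The parity statement for CC covers visit schedule, comorbid conditions and handouts. It does not cover progress reports.
- The Section 12 provision covers physical measures, with consent. It carries no behavioural recommendations.
- The retention subsection makes PCPs supporters of both interventions. The monitoring reports it mentions go to participants.
- The delivery-systems subsection invites all PCPs at the sites and gives them the same brief training.

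None of these gives CC participants' PCPs a progress report with recommendations to reinforce.

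**Step 3: is the report part of the intended contrast?** The overview in Section 11 says the arms differ principally in their view of the form in which calories are eaten. The theory subsection adds MyP's emphasis on environmental cues. Neither lists clinician feedback.

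**Step 4: can the analysis remove it?** Section 4 says analyses will account for nesting within clinics and providers. That does not help, because the report would differ by arm among patients of the same provider.

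**Step 5: who prepares the report?** The MyP paragraph says only research staff. Section 7 uses that term for the people who approach patients in the waiting room ("The research staff will then introduce the study to the patient"), and the same passage calls them research assistants, a group Section 10 says is to be masked. Against that, Section 11 has community health workers record session and adherence data in REDCap, and Section 12 refers to unmasked staff for adverse-event follow-up. So unmasked people exist who could write the reports, but no section assigns the task to them.

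**Step 6: size.** The power section implies planned weight differences of 7.9 − 6.4 = 1.5 kg and 5.4 − 3.4 = 2.0 kg. These could serve as a denominator. Nothing in the documents gives the effect of a PCP report on weight or any other outcome, so there is no numerator and no percentage can be given.

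**The case against.** The strongest reply is that exclusivity is inferred from silence. No sentence says reports are withheld from CC, and several describe PCP involvement as common to both arms. The two paragraphs look loosely drafted, as the screening-visit wording shows. This stands as a limit: the point concerns what the plan provides as written, and CC participants' PCPs may in practice have received something similar. It does not remove the point, because two parallel paragraphs make the silence meaningful and a plan should not leave the matter to inference.

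A second reply is that the arms already differ openly as packages. MyP adds taste-testing, half an hour more in each group session by one description, and more emphasis on the home environment. A brief report is one further element. This also stands in part. A reader might infer that any MyP advantage could not be attributed to the dietary approach, but that is too strong: attribution is weakened, and the report is one contributor among several. Those other differences are, however, declared features of the MyP approach, and the report is not.

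A third reply concerns masking. A reader might infer that outcome assessors are unmasked by preparing the reports. The documents do not say so. They do not identify the preparers, and unmasked personnel exist. What remains is a risk created by an unspecified role.

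Finally, a reader might take the recommendations to be individually tailored, or assume that every MyP participant is reached. The text calls the recommendations key, not tailored. Exposure depends on routine visits, whose number is not given, and on PCPs who are invited to take part.

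**Conclusion.** The point holds in limited form. Followed as written, the plan supplies a clinician-reinforcement component to MyP and gives no equivalent to CC. The component lies outside the stated contrast, and the protocol's own reasoning treats such support as active. It could contribute to between-arm differences in self-efficacy, satisfaction or weight, by an amount the documents do not allow to be estimated.

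This rests on two assumptions: that the CC paragraph's silence means no report is sent, and that PCPs act on the reports they receive. If CC participants' PCPs receive the same type of report, the co-intervention concern falls away and only the wording needs correcting. The masking element is a risk that depends on who prepares the reports. It is not a demonstrated breach. The change is worth making because it removes an avoidable difference between the arms at little cost.

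**What to change.** 1. Send the same type and frequency of progress report, with arm-appropriate content, to PCPs in both arms, or send none in either arm. State the choice in both PCP-role paragraphs of Section 11.
2. Specify that unmasked intervention staff, not outcome assessors, prepare the reports, and cross-refer to the masking rules in Section 10.
3. If reports have already been issued to one arm only, say what each arm received, describe the report as part of the MyP package, and limit attribution to the dietary approach accordingly.

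Cost: a second report template and the clerical work of issuing it for about 130 CC participants (261 / 2 = 130.5, assuming equal allocation). Dropping the report in both arms avoids that work but loses the PCP reinforcement in MyP. If CC reports were always intended, one added sentence in the CC paragraph closes the co-intervention gap; step 2 is still needed to name the preparers.

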
While both the DPP and DASH dietary approaches have been shown to reduce excess body weight in the short run, the ability of patients to maintain these approaches for the long-term remains to be determined. Several steps were taken to ensure that the intervention effects for the MyP condition would be long-lasting.

Additional steps incorporated in the current proposal to ensure sustainable intervention impact.

We will take several steps to ensure that the intervention effects for the MyP condition would be sustainable by the community clinics. One step is to replace the masters or doctoral-level health

Patterned after protocol published online in association with Appel et al. (2011)¹⁵

educators/counselors typically used in behavioral weight loss interventions³² with trained community health workers (promotoras). The social modeling of Social Cognitive Theory^{33,34} and experience³⁵ suggest that the predominantly low income Latino immigrant patient population comprising the study population can relate to non-college-educated Latino community health workers better than they can to bilingual but non-Latino masters or doctoral-level counselors.³⁵ African American type 2 diabetes patients as well as Latino patients have benefited from use of community health workers as behavior change agents.^{36,37} On the other hand, community health workers need substantially more training and supervision to carry out the intervention according to protocol. Substantial time is devoted in Year 1 of the present proposal to the training of the community health workers. The Intervention Director's primary responsibility during the active intervention phase is to supervise the community workers in the MyP condition weekly, monitor their lifestyle coaching, and provide guidance as needed to ensure adherence to the MyPlate.gov messages. TCC nutritionists will supervise the community health workers weekly in the CC condition to ensure good adherence to the CC intervention protocol. The use of coaches with closer community ties to the participants holds promise for more sustained lifestyle behavior change benefit.^{36,38-40}

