¹ Accrual took longer than expected. Planned subgroup analyses by sex and ethnicity requiring the original sample size were obviated by the recruitment of fewer men than anticipated (4.6% versus 30% expected) and fewer African Americans than expected (7.7% versus 15% expected). Statistical power for remaining planned subgroup analyses involving women and Latinos exceeded 80% at the lower sample size of N =261.

Patterned after protocol published online in association with Appel et al. (2011)¹⁵

enrolling mostly women. Randomization will occur at the individual level despite the risk of patients assigned to different conditions talking to each other in the waiting room and discovering that their health coaching messages are different. Except for brief encounters with trained clinical staff about their participation in the lifestyle change coaching program, most of the health information transmitted in this program will occur in the home, by phone or in group education classes, not in the examination room. Analyses will take into account the fact that patients are nested within clinics and within providers but previous experience with randomization at the clinic level convinced us that the study design was stronger, easier to administer and easier to analyze when randomization occurred at the level of the individual patient instead of at the level of the primary care clinic.

The Community Advisory Board. The Community Advisory Board (CAB) is comprised of members representing all major stakeholders: UCLA investigators, TCC investigators, TCC patient representatives, community public health leaders, thought leaders in lifestyle change interventions. The CAB can be viewed as equivalent to the Board of Directors. Members' input will help shape the design of the proposed research, interpretation of results and the nature of the final recommendations, but will generally leave the day-to-day decision-making to the TCC and UCLA investigators. Members with equivalent ability to represent specific stakeholders with respect to community approaches to weight control will be selected to replace those who can no longer serve on the CAB, with the objective of continuing to represent fairly the full range of stakeholders. Study investigators are part of the CAB because their presence validates the stated authority of the CAB to make decisions about study implementation, interpretation of results and final recommendations.

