13. STATISTICAL POWER AND SAMPLE SIZE ESTIMATION

Hypotheses for the Two-Group Randomized Control Trial Design: The aim is to conduct an RCT of the impact of CC versus MyP on patient-centered outcomes in up to eight community clinic sites in Long Beach. Participants will include: 150 patients randomly assigned to receive

Patterned after protocol published online in association with Appel et al. (2011)¹⁵

CC from trained health coaches, another 150 patients assigned to receive MyP from another group of trained health coaches over the course of 12 sessions in six months.

Intervention check: Does exposure to MyP versus CC lead to increased patient reports of fruit and vegetable intake in MyP? A preliminary check will be made to confirm that one of the defining features of the MyP approach, namely a doubling of F&V intake, was reflected in study participants' daily intake of F&V assessed at follow-up. If no difference were observed in F&V assessed at follow-up then the validity of the experimental contrast would be jeopardized. There could still be experimental effects, but the causal mechanisms would be unknown. Because numerous studies have succeeded in getting patients to double their intake of F&V for up to four years, a negative outcome of this intervention check is unlikely.²⁵

Question: Does exposure to MyP versus CC lead to decreased patient 12-months reports of daily hunger ratings/ daily meal satisfaction ratings/ daily fullness ratings in MyP during a time when patients were trying to lose excess weight (primary)? Will exposure to MyP versus CC lead to increased patient weight control self-efficacy, patient quality of life and patient satisfaction with her/his weight control program (primary)?

Question: Will exposure to MyP versus CC lead to increased weight loss/ reduced waist circumference equally for both conditions sustained for 12 months (secondary)?

Avoidance of bias. Covariates and effect modifiers. Standard demographic variables, including gender, age, ethnicity, marital status, and educational attainment will be included as covariates. Possible effect modifiers will also be included as covariates, including language preference (English / Spanish), last month food security, meal-skipping status, and daily physical activity level.

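### The weekly coach meeting in section 11 covers dietary problem-solving for both arms, against the arm-specific supervision in section 3, and leaves an avoidable route for contamination

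*Combined protocol and SAP*

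**What the plan says.** Section 3, in the steps for sustainable impact, assigns supervision by arm. The Intervention Director's "primary responsibility during the active intervention phase is to supervise the community workers in the MyP condition weekly". For the other arm, "TCC nutritionists will supervise the community health workers weekly in the CC condition to ensure good adherence to the CC intervention protocol". Section 13 describes separate delivery teams: patients are to receive "CC from trained health coaches, another 150 patients assigned to receive MyP from another group of trained health coaches". Section 10 fits this, since each coach looks up the participants of his or her own condition.

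Section 11, under Standardizing Delivery of the Intervention, reads differently. It says: "The lifestyle change coaches will meet weekly with the Intervention Director as part of a weekly" Learning Community, whose task is to "solve how to get patients to adhere better to both the dietary and the physical activity prescriptions in the CC and MyPlate conditions". The Director is also to learn from the coaches' "weekly debriefings which solutions to lifestyle change challenges are effective". Neither sentence separates the arms.

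Three other places bear on the same question:
- Section 11, on the coaching sessions, gives another account of supervision, by the clinic's health education department.
- Section 11, on fidelity and on missed visits, gives the Intervention Director weekly case management and takes referrals from both arms.
- Section 12 describes a weekly meeting of investigators and coaches, on adverse events among other topics.

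The only contamination that the plan discusses is between patients. Section 4 says: "Randomization will occur at the individual level despite the risk of patients assigned to different conditions talking to each other in the waiting room". It accepts that risk because most content is delivered at home, by telephone or in classes.

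**The concern.** The reason given in section 4 for accepting contact between patients places the content with the coaches. If coaches from both arms discuss each week what helps patients keep to either diet, dietary advice can cross at its source, and the plan does not consider this.

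Section 11 says that the arms differ mainly on the form in which food is eaten. MyP limits juice and favours whole produce; CC treats the source of calories as immaterial. The CC goal is 5 daily servings of fruit and vegetables with juice counted, and Table 6 sets 7 to 12 for MyP. A CC coach who picks up advice on whole produce in place of juice, or on widening the variety of produce, would narrow that difference.

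The bias is not conservative throughout. It would pull the hunger and systolic blood pressure comparisons towards no difference. For body weight, section 2 hypothesises similar declines in the two arms, and dilution would make that result easier to reach for the wrong reason.

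**Working it through.** **Side-by-side reading**

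| Question | Section 3 | Section 11, Standardizing Delivery |
|---|---|---|
| Who meets the CC coaches weekly? | Clinic nutritionists | Intervention Director, if the unqualified term for coaches includes them |
| Who meets the MyP coaches weekly? | Intervention Director | Intervention Director |
| Dietary scope | One arm per supervisor | Both conditions |
| Rule on sharing between arms | None stated | None stated |

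The meeting covers both diets and its attendees are not limited by arm, so a shared meeting is the natural reading. Even if the two groups were seen separately, the person whose main duty is MyP would be guiding delivery of the CC diet, which section 3 gives to the nutritionists.

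**Existing safeguards**

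- Corrective feedback when coaches depart from protocol, certification, leader guides and direct observation (section 11). These test adherence to each arm's protocol. None is said to look for material from the other arm.
- Computer-driven calls (section 11). These cover telephone sessions, within which individual problem-solving remains open.
- The fruit-and-vegetable check (section 13). The plan itself says that no difference would undermine the contrast. The check uses follow-up data, at 6 months at the earliest, while Table 7 places the sessions in months 1 to 3. It can detect a lost contrast but not prevent one.

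**Illustration of size**

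Inputs from section 13: d = (53.5 − 46.7)/13.2 = 6.8/13.2 = 0.515, stated as 0.52; two-sided alpha 0.025 (z = 2.241); power 0.80 (z = 0.842); attrition 20%. From section 4: N = 261. The share c of the contrast that is lost is not in the documents and is assumed.

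1. Reproduce the plan's figure. n per arm = 2(2.241 + 0.842)²/d² = 19.01/d². With d = 6.8/13.2 this is 71.6, so 72 per arm and N = 144, which matches the plan. With d = 0.52 it is 70.3, so 71 per arm and N = 142. The match holds only if the stated rho of .85 is not used. As a baseline adjustment it would give 70.3 × (1 − 0.7225) = 19.5, so 20 per arm and N = 40.
2. Numbers analysed: 261 × 0.80/2 = 104.4, taken as 104 per arm. The plan states the 20% for 6 months; it is assumed here to hold at 12.
3. Diluted effect: d(1 − c). Required N rises by 1/(1 − c)², which is 1.23 at c = 0.1 and 1.56 at c = 0.2.
4. Power = Φ(d(1 − c)√(104/2) − 2.241), with √52 = 7.211.

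| c | d(1 − c) | Required N | Power, 104 per arm |
|---|---|---|---|
| 0 | 0.520 | 142 | Φ(1.51) = 0.93 |
| 0.1 | 0.468 | 174 | Φ(1.13) = 0.87 |
| 0.2 | 0.416 | 220 | Φ(0.76) = 0.78 |

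Power reaches 0.80 when d(1 − c) = (2.241 + 0.842)/7.211 = 0.428, so c = 1 − 0.428/0.52, about 18%.

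**The case against.** The strongest reply is that the text is unclear rather than contradictory. A primary responsibility does not exclude other duties. Section 11 does not say that its meeting replaces the nutritionists' supervision, nor that both groups of coaches sit in one session. A reader might infer both; the documents state neither. This stands, and the point is limited to the natural reading and to the absence of a rule.

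It is also tempting to treat what coaches say as the whole contrast. It is not. Taste-testing is for MyP only; numeric calorie goals, the calorie guide and the supplied meal plans are for CC only; recipes and self-monitoring tasks differ by arm. A meeting would not readily transfer these. Table 8 also fixes arm-specific topics for all 11 sessions, which limits how far a borrowed tip can travel.

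Home-environment advice is a poor example of leakage. The abstract puts such changes in both arms and Table 8 gives CC a home audit. Sections 2 and 11 elsewhere treat it as a MyP feature, which is a separate inconsistency.

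Finally, the dilution is assumed. Zero loss is possible, and hunger power stays above 0.80 until about 18% of the contrast is lost. This stands too. What the reply does not answer is that no passage keeps dietary solutions within an arm, and that the safeguards are not directed at this route.

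**Conclusion.** The concern holds as a risk with a known direction and an unknown size. Sections 3 and 13 keep supervision and coaching separate by arm; section 11, read naturally, pools weekly dietary problem-solving under the MyP supervisor without any limit on sharing. Any transfer would weaken the hunger and systolic pressure comparisons and favour the hypothesis of similar weight loss.

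A reader might infer that contamination took place, or that the trial is underpowered because of it. The documents support neither. The power figures are illustrative. They rest on an assumed loss of contrast, on 20% attrition applied at 12 months, and on the plan's own sizing for hunger with no gain from baseline adjustment. With such a gain, the same loss would cost less power. This is a cheap improvement, not a flaw that invalidates the design.

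**What to change.** - Reconcile the statements on supervision in section 3 and in section 11 (coaching sessions; Standardizing Delivery), and say who attends and who leads each weekly meeting.
- Hold dietary problem-solving and debriefing separately by arm, under the supervisors that section 3 already names.
- Limit any joint session to content common to both arms: physical activity, retention and safety.
- Apply the same separation to dietary content in case management (section 11) and in the weekly investigator and coach meeting (section 12).
- Record any dietary content from the other arm in the fidelity observations already planned.

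The cost is one weekly meeting split into two, with some scheduling effort and less shared learning between the coach groups. No new staff are needed. If coaching has already been delivered, what remains is to state how the meetings were run and to report what the fidelity observations show.
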